1.0 Background

Benign prostatic hypertrophy (BPH) is common with almost 50% of men having pathologic changes in the prostate between 50 and 60 years old¹. There are many options for the treatment of BPH, though a minimally invasive approach has been favorable over the past decade. Enucleation of a prostate with a laser has become a mainstay of BPH treatment and has shown to be safe and effective. Traditionally, a holmium laser is used for this (i.e. Holmium laser enucleation of the prostate or HoLEP), though recent new technologies have been developed to improve laser surgery. One example is the Moses laser fiber produced by Lumenis (Yokneam, Israel), which alters laser pulse wave characteristics to improve the efficiency of energy delivery to a target. The technology is hypothesized to lead to better improvements in operative time and hemostasis ^{2,3,4}. Though the technology has been proven to be safe in human use, it has not been formally evaluated for prostatic enucleation. We seek to compare HoLEP to Moses laser enucleation of the prostate (i.e. MoLEP) for the treatment of BPH.

1. Berry SJ, Coffey DS, Walsh PC, Ewing LL. The development of human benign prostatic hyperplasia with age. *J urol* 1084; 132(3):474-479.
3. Mark Cynk, Holmium Laser Enucleation of the Prostate is More Efficient with More Laser Power, abstract #MP7- 01, Moderated Poster Session 7: BPH/LUTS, WCE 2016

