5.0 Enrollment/Randomization

We will identify patients scheduled to undergo laser enucleation of the prostate for BPH through our urology clinic. Power analysis to detect a 50% change in blood loss (i.e. a change in hemoglobin level) will lead to approximately 20 patients in each group. A random number generator will be used at the beginning of each case after the induction of anesthesia to randomize patients to MoLEP or HoLEP.

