Vanderbilt University Medical Center
Department of Urologic Surgery
[REDACTED]
[REDACTED]

Statistical Analysis Plan
Date: 12/21/2021

NCT04263987

**Evaluation of the Moses Laser for Prostate
Enucleation**

[name]

Clinical Instructor of Urologic Surgery
Vanderbilt University Medical Center
Department of Urologic Surgery

Power and Statistical Analysis

Power analysis was performed for sample size estimation based on prior reports from the literature, which previously estimated a 20% improvement in operative time when performing M-HoLEP. A sample size of 60 subjects had greater than 80% power to detect this change with $\alpha=0.05$. Continuous and categorical variables were compared using the Student T-test (2-tailed) and Fisher exact test, respectively. Multiple linear regression was performed to evaluate for the effect of the MOSES technique on operative time controlling for age, Charlson comorbidity index, change in hematocrit, and the amount of prostatic tissue enucleated. All testing was performed with $p < 0.05$ as significant. All analyses were conducted in Stata 14.2 (StataCorp, College Station, Texas).

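### The SAP's only regression for the laser's effect on operative time adjusts for two post-randomisation measures, so its coefficient need not be the time the laser saves

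*SAP*

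**What the plan says.** **Randomisation.** Protocol section 5.0: "A random number generator will be used at the beginning of each case after the induction of anesthesia to randomize patients". Allocation therefore precedes enucleation.

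**Expected effects of the laser.** Protocol section 1.0: "The technology is hypothesized to lead to better improvements in operative time and hemostasis". Section 2.0 lists blood loss beside operative time and quality of life as things to compare, without ranking them.

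**Analysis.** The SAP's one model is a linear regression of operative time on laser arm, fitted "controlling for age, Charlson comorbidity index, change in hematocrit, and the amount of prostatic tissue enucleated". For group comparisons in general it states: "Continuous and categorical variables were compared using the Student T-test (2-tailed) and Fisher exact test, respectively". On the threshold: "All testing was performed with $p < 0.05$ as significant". Neither document names a primary outcome or a deciding analysis. Section 6.0 of the protocol records total surgery, enucleation and morcellation times; the SAP does not say which of them is its operative time.

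**Sample size.** Protocol section 5.0 begins "Power analysis to detect a 50% change in blood loss (i.e. a change in hemoglobin level" and arrives at about 20 patients per group. The SAP takes a 20% improvement in operative time and says: "A sample size of 60 subjects had greater than 80% power to detect this change".

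**The concern.** In a randomised comparison, the arms are alike on average in everything fixed before allocation. Adjusting for such variables leaves the target of estimation in a linear model unchanged and may sharpen it. A variable that arises after allocation has no such guarantee. If the laser changes it, and it is related to operative time, the regression compares patients made equal on something the laser altered.

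Hematocrit change is the clear case here, because the protocol hypothesises better hemostasis and was itself sized on hemoglobin change. The amount of tissue enucleated is weaker: no passage suggests that the laser alters it, but it too is known only after allocation.

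At stake is the headline quantity. The SAP is powered for a 20% improvement in operative time, which is a total effect. If the regression coefficient is read as that quantity, it may be too small or too large. If the t-test and the regression disagree, the plan gives no basis for saying which one carries the conclusion.

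**Working it through.** **1. When each covariate becomes known**

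| SAP covariate | Known at randomisation? | Do the documents expect the laser to affect it? |
|---|---|---|
| Age | Yes | No |
| Charlson index | Yes | No |
| Change in hematocrit | No: needs the postoperative blood count (protocol 6.0) | Yes: hemostasis (1.0), blood loss as an aim (2.0), sizing on hemoglobin change (5.0) |
| Tissue enucleated | No: a result of the operation | Not stated |

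**2. The two power statements.** Neither can be reproduced, because no mean, SD or coefficient of variation (CV) is given. They can be inverted with the noncentral t distribution, assuming two-sided 0.05, exactly 80% power and equal arms (the protocol states neither alpha nor power).

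- SAP, 30 per arm: detectable standardised difference d = 0.736. A 20% change then needs CV = 0.20/0.736 = 27%.
- Protocol, 20 per arm: d = 0.909. A 50% change needs CV = 0.50/0.909 = 55%.

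Each is attainable, so neither is shown to be wrong. They differ in endpoint, effect and total (about 40 against 60). If 60 subjects give exactly 80% power for operative time, 40 give 62%.

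**3. Bias in the estimate.** Measure time and hematocrit change in within-arm SDs. Let r be their within-arm correlation and s the laser's shift in hematocrit change. In a linear model

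adjusted effect = total effect − r × s.

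This algebra holds whatever produces the correlation. It also holds with tissue in the model, provided that tissue is unrelated to hematocrit change within arm and not shifted by the laser. Assume a true saving of 20% = 0.736 SD.

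| s | r | r × s | Share of 0.736 | 20% appears as | Opposite direction |
|---|---|---|---|---|---|
| 0.25 | 0.3 | 0.075 | 10% | 18.0% | 22.0% |
| 0.25 | 0.5 | 0.125 | 17% | 16.6% | 23.4% |
| 0.50 | 0.3 | 0.150 | 20% | 15.9% | 24.1% |
| 0.50 | 0.5 | 0.250 | 34% | 13.2% | 26.8% |

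First row: 20 × (1 − 0.075/0.736) = 18.0. With s = 0 the estimate stays at 20%.

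**4. No total effect on time.** The adjusted coefficient then centres on −r × s rather than zero. In simulation (30 per arm, normal data, at least 20,000 trials per row), the adjusted test at 0.05 rejects in about 6, 8, 9 and 18–19% of trials for the four rows above. If tissue is also in the model and explains 40% of the variance in time, residual noise falls and the figures are about 7, 12, 12 and 33–34%. With s = 0, both versions reject in about 5%.

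**5. What dropping tissue costs.** If tissue explains a share R² of the variance in time, the t-test's interval is wider than the tissue-adjusted one by the factor 1/√(1 − R²): 1.12, 1.29 and 1.58 at R² = 0.2, 0.4 and 0.6. Adjusting instead for preoperative size, with an assumed correlation of 0.8 with tissue, gives √[(1 − 0.64R²)/(1 − R²)] = 1.04, 1.11 and 1.24.

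**The case against.** **An unadjusted comparison is already there.** The SAP's general sentence on continuous variables would naturally cover operative time, so the regression may be supplementary. This largely stands. A reader might infer that the regression is the trial's only estimate of the effect on time; the documents do not support that. What remains is that neither analysis is designated as deciding.

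**Tissue enucleated stands in for gland size and buys precision.** Also fair. A reader might infer that the adjusted test is the less powerful one. That cannot be concluded from the documents. With tissue explaining an assumed 20–60% of the variance in time, adjusted power in the four scenarios runs from about 66% to nearly 100%, mostly above the t-test's 80%. The harm lies in what is estimated, not in a demonstrated loss of power. Protocol section 6.0 also records prostate size, which could serve the same purpose if measured before surgery.

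**The coefficient could be useful as a direct effect.** A reader might take it as the laser's effect on time with the bleeding route removed. That needs hematocrit change to precede operative time and share no unmeasured cause with it. The blood count is postoperative, so a longer operation may itself lower hematocrit, or a difficult gland may cause both. The coefficient is then neither the total effect nor a clean direct effect.

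**The sizes are assumed.** True. The documents give no SDs, correlations or shifts, and the bias vanishes if the laser leaves both covariates unchanged.

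**Conclusion.** The concern holds for the regression as written. It conditions on two measures that arise after allocation, one of which the protocol expects the laser to change. Its coefficient therefore need not equal the laser's total effect on operative time. The structural fault follows from the text alone; its size and direction do not. The illustrative distortion is a few percentage points of a 20% saving, up to about a third of it at the larger end (13% or 27% in place of 20%). The test can also reject well above 5% when the laser has no total effect on time. All of this rests on the assumed shift of 0.25–0.5 SD, correlation of 0.3–0.5, 30 per arm and exactly 80% power.

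The unreconciled sample-size statements are a separate inconsistency. A reader might infer that 60 is too few, but the inputs needed to judge that are absent. A reader might also infer a particular inflated error rate from testing every outcome at 0.05; the plan states no rule by which any single significant result would establish benefit, so no such figure can be attached to it. The point should be corrected, but does not invalidate the trial.

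**What to change.** 1. Rest the conclusion on operative time on an analysis free of post-randomisation covariates. Either the t-test already in the SAP, or a regression on arm, age, Charlson index and the prostate size recorded under protocol section 6.0, would do. For the latter, first confirm that the size is the preoperative measurement. Say which recorded time is the outcome.
2. Label the regression containing change in hematocrit and tissue enucleated as exploratory, and do not read its coefficient as the time saved by the laser.
3. The SAP is written in the past tense, so state when the deciding analysis was chosen. If that was after the data were seen, label it post hoc; this applies equally to the t-test and to the regression. Report all operative-time analyses.
4. Reconcile protocol section 5.0 with the SAP: say which endpoint the sample size rests on, and when and why the target moved from about 40 to 60.

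**Cost.** Text only; no new data or procedures. The price is precision: under the assumptions in the last step of the working, the t-test's interval is 12–58% wider than the tissue-adjusted one, and preoperative size recovers much of that (4–24% wider). If the data have already been analysed, naming the deciding analysis now makes the report more transparent but does not restore error control.

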2.0 Rationale and Specific Aims

The aims of this study are to:

1. Evaluate Moses laser technology for prostatic enucleation compared to traditional holmium laser enucleation.
2. Determine changes in blood loss, operative times, and quality of life improvements between the two technologies.

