6.0 Study Procedures

Patients will be consented in our clinic after being scheduled for surgery. All patients will fill out voiding symptom scores (i.e. International Prostate Symptom Scores(IPSS)), erectile dysfunction symptom scores (i.e. Sexual Health Inventory for Men(SHIM)) and have a preoperative urine flow, postvoid volume and a prostate specific antigen (PSA) recorded. Intraoperatively, total surgery time, as well as enucleation and morcellation times, will be recorded. Furthermore, intraoperative blood loss and surgical complications will be evaluated. Postoperatively, all patients will be observed overnight in the hospital with a urethral catheter. Routine labs will be sent including a complete blood count and metabolic panel. Postoperative day one, all patients will undergo a voiding trial for catheter removal. Patients will be monitored for routine complications after HoLEP such as urinary retention, urosepsis, urinary leakage. Other variables to be recorded will be age, sex, size of prostate, BMI, anticoagulation status, and other comorbidities. Patients will follow up at 4 weeks for a postoperative check and evaluation of symptoms (i.e. IPSS, SHIM, flow rate, postvoid residual volume and PSA).

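### The SAP calls every test significant at p<0.05 over about nine or ten outcomes with no primary outcome or hierarchy, so the chance of some false significant difference is about 27–40% (false benefit about 13.5–22%)

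*SAP*

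**What the plan says.** The SAP's threshold rule is a single sentence: "All testing was performed with $p < 0.05$ as significant". The tests it governs are described only by type of variable: "Continuous and categorical variables were compared using the Student T-test (2-tailed) and Fisher exact test, respectively". The SAP lists no outcomes. It also fits a multiple linear regression for operative time, so that outcome is analysed twice.

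No outcome is called primary in either document. Protocol section 2.0 puts three domains side by side: "Determine changes in blood loss, operative times, and quality of life improvements between the two technologies". The two sample-size statements rest on different outcomes. Protocol section 5.0 uses hemoglobin: "Power analysis to detect a 50% change in blood loss (i.e. a change in hemoglobin level) will lead to approximately 20 patients in each group". The SAP uses operative time, citing literature that "previously estimated a 20% improvement in operative time when performing M-HoLEP".

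The outcomes have to be gathered from protocol section 6.0. During surgery, "total surgery time, as well as enucleation and morcellation times, will be recorded", along with blood loss and complications. At four weeks there is "evaluation of symptoms (i.e. IPSS, SHIM, flow rate, postvoid residual volume and PSA").

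**The concern.** Under the SAP's rule each comparison carries its own 5% error rate, and any of them that falls below 0.05 may be called significant. Nothing marks one comparison as the trial's answer and the rest as supporting. With nine or ten outcomes and equivalent lasers, the chance that some outcome crosses the line is well above 5%. A reader of the report could not tell a planned finding from the one that happened to cross.

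This is separate from the disagreement over which outcome sized the trial. Naming one sizing outcome would still leave a rule under which an isolated p<0.05 on, say, SHIM or morcellation time counts as a significant difference between the technologies.

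**Working it through.** **The plan's own figure.** The SAP says "A sample size of 60 subjects had greater than 80% power to detect this change with $\alpha=0.05". No standard deviation is given, so this cannot be reproduced exactly. Assuming 30 per arm and a two-sided test, 80% power for a 20% difference needs a coefficient of variation (CV) of at most

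0.20 / [(1.960 + 0.842) × √(2/30)] = 0.276 (0.272 with the noncentral t).

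Power is about 86–87% at a CV of 0.25 and 72–73% at 0.30. The statement is attainable but cannot be verified. It concerns one comparison, operative time, and says nothing about the set of tests.

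**Counting the outcomes.**
- Times (protocol 6.0): total, enucleation, morcellation — 3
- Bleeding: intraoperative blood loss (6.0) and hemoglobin change (5.0) — 2, or 1 if they are the same quantity, because section 5.0 explains blood loss as a change in hemoglobin
- Four-week measures (6.0): IPSS, SHIM, flow rate, postvoid residual, PSA — 5

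The total is nine or ten continuous outcomes. Complications are left out: at a 5% event rate with 30 per arm, Fisher's exact test has a true size of only about 0.15%. The second (regression) analysis of operative time is also left out.

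**Independent tests, all nulls true.** A two-sided test at 0.05 gives a false result in either direction with probability 0.05, and in Moses's favour with probability 0.025.
- Either direction: 1 − 0.95⁹ = 37.0%; 1 − 0.95¹⁰ = 40.1%
- Benefit only: 1 − 0.975⁹ = 20.4%; 1 − 0.975¹⁰ = 22.4%

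**Correlated tests.** The documents give no correlations. The table assumes jointly normal test statistics with one common pairwise correlation ρ, evaluated by numerical integration.

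| ρ (assumed) | Any difference, 9 tests | Any difference, 10 tests | Benefit only, 9 tests | Benefit only, 10 tests |
|---|---|---|---|---|
| 0 | 37.0% | 40.1% | 20.4% | 22.4% |
| 0.3 | 32.6% | 35.1% | 16.5% | 17.8% |
| 0.5 | 26.9% | 28.7% | 13.5% | 14.4% |
| 0.7 | 20.2% | 21.3% | 10.1% | 10.7% |
| 0.9 | 12.4% | 12.8% | 6.2% | 6.4% |

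**Uneven correlation.** Total time contains the component times, so one common ρ is a simplification. A simulation used correlations of 0.7–0.8 among times, 0.7–0.9 between the two bleeding measures, 0.3–0.5 among four-week measures and 0.1–0.3 between groups. All of these are assumptions. The chance of any false difference was about 28–33% for nine outcomes and 30–35% for ten, inside the range for ρ between 0.5 and 0.

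**The case against.** A reader might take the 27–40% as the chance of a false *benefit* for Moses. The SAP's t-test is two-tailed, so half of those false results would favour standard HoLEP on any one outcome. The benefit-only range is about 13.5–22%, and its benchmark is 2.5%, not 5%. This objection stands, and the two figures must be kept apart.

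The count is an inference. The SAP lists no outcomes, and protocol section 6.0 says what will be recorded or evaluated, not what will be tested as an efficacy endpoint. This also stands, but going from ten to nine lowers the independent figure only from 40% to 37%.

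A reader might also infer that the plan promised 5% overall control and broke the promise. It did not: in the SAP, α=0.05 belongs to the operative-time power statement.

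The SAP is dated 12/21/2021 and is written in the past tense, which may suggest that a favourable outcome was chosen after the results were known. The documents do not show this. They show only that the rule would not prevent it. The same uncertainty limits the remedy, because an order set after results are seen cannot claim 5% control.

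Finally, formal gatekeeping in a 60-patient trial is partly a matter of preference. That is fair for the secondary outcomes, where an exploratory label is enough. It does not excuse having no designated main test.

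**Conclusion.** The concern holds in a limited form. The SAP applies one unadjusted threshold to every test, with no primary outcome, hierarchy or exploratory label, over about nine or ten inferred continuous outcomes. If the lasers are truly equivalent on all of them, at least one false significant difference is expected in about 27–40% of such trials for assumed correlations of 0.5 to 0, and in about 20–21% at 0.7. A false benefit alone is expected in about 13.5–22%, roughly five to nine times the 2.5% of a single test (13.5/2.5 = 5.4; 22.4/2.5 = 9.0).

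Stronger correlation lowers these figures, and more tested outcomes would raise them. The data and the individual comparisons are not invalidated. What needs repair is the rule for what may be claimed.

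**What to change.** Replace the SAP's threshold sentence with a rule along these lines:

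1. One confirmatory test at two-sided 0.05: total operative time, by one stated analysis. The two-tailed t-test already in the SAP is the simpler choice, because the regression adjusts for change in hematocrit and tissue removed, both of which arise after randomisation. The SAP says only operative time, so the sponsor should confirm that total time is the measure behind the 20% assumption.
2. Reconcile this with protocol section 5.0, which sizes the trial on hemoglobin change at about 20 per group (about 40 in all), against the SAP's 60 on operative time. State which governs and why.
3. Optionally, test hemoglobin change at 0.05 only if the first test is significant. A sequence fixed in advance holds the family-wise error of these two claims at 5% and costs the first test no power.
4. Report everything else, including the alternative operative-time analysis, with estimates and 95% confidence intervals, labelled exploratory and not called significant.
5. State whether any results had been seen when the order was set. If so, call it post hoc and do not claim 5% family-wise control.

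This needs no more patients or data. It takes new SAP wording and the reconciliation with the protocol. The price is that a nominal p<0.05 on a component time, IPSS, SHIM, flow rate, postvoid residual or PSA can no longer be claimed as a finding.
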